### Medical records from UW Health or other sources

The study team has authorized access to electronic medical records and will access participant data as allowed by legal medical record holder. Record review will be reviewed initially at screening, after each study visit for participants who consent, and at study completion.

## **18.0 Sharing of Results**

### Describe whether results will be shared with participants or others

The results of the urine pregnancy test and physical exam results will be added to the participant's medical record.

Individual study results will not be shared. Study results will be shared with participants in aggregate as a results brief.

### Describe plans to share study results with the public.

Study results have the potential to be submitted for publication to a peer-reviewed scientific journal. Study results may also be presented at professional conferences and at departmental meetings.

## 19.0 Data Banking

### Data banked for future use

Data will be accessed in REDCap until study publication. Study investigators will have access to data. After study publication, de-identified data will be stored on a secure department server for future use.

### Data to be stored

- Survey data (coded):
  - a. Bristol Stool Scale
  - b. St Mark's (Vaizey)
  - c. FIQoL
  - d. PISQ-IR
  - e. PGI-I
  - f. Patient satisfaction

- g. Estimated percent improvement
- h. MAUQ
- i. PFDI-20
- Exam data (coded):
  - a. Vitals (height, weight, pulse, blood pressure)
  - b. POP-Q
  - c. Brink Scale Score
- Coded patient demographic and relevant medical history data

### Procedures to release data

Data may be shared with researchers at UW-Madison, Axena Health or other outside institutions for future research. This research will be about fecal incontinence or other types of research. Data will be kept for an unlimited amount of time after completion of this study. IRB review will be requested before data is used for research outside the scope of this protocol. PHI will be removed from the data before sharing with other researchers.

### Participants may withdraw their banked data from future research use.

If a participant withdraws from the study, they will be asked if collected data can be utilized or withdrawn from the banked data. Data will still be part of the study records. Participants will be asked if they can be contacted in the future and if the study team can contact them in the future.

Participants will keep or dispose of the study device.

After any study analysis, participants will not be able to request data withdrawal. Participants will be made aware that analyzed data cannot be withdrawn.

## 20.0 Study Analysis

### **Statistical Hypotheses**

This is a prospective, pragmatic, non-inferiority randomized control trial.

- Primary alternate hypothesis: 8 weeks of use of the Leva Pelvic Health System is non-inferior to 16 weeks of use for the treatment of fecal incontinence in women assessed by the St.Mark's/Vaizey score at 16 weeks follow up.

-Primary null hypothesis: 8 weeks of use of the Leva Pelvic Health System is not non-inferior to 16 weeks of use for the treatment of fecal incontinence in women assessed by the St.Mark's/Vaizey score at 16 weeks follow up.

-Secondary endpoints:

- To determine the impact of using the Leva Pelvic Health System on the following parameters and to compare these between 8 vs 16 weeks of use at 16 and 24 weeks:

- POP-Q
- Brink Scale Score
- Stool consistency (Bristol Stool Scale)
- Fecal Incontinence Quality of Life (FIQoL)
- Sexual Function (PISQ-IR)

- Patient Global Impression of Improvement (PGI-I)
- Patient Satisfaction
- Perceived Percentage of Improvement
- Global Pelvic Floor Symptoms (Pelvic Floor Distress Inventory PFDI-20)
- To evaluate change (improvement) from baseline to 24 weeks after 8 or 16 weeks of treatment as assessed by St.Mark's/Vaizey score
- To evaluate the relationship between adherence to the Leva Pelvic Health System treatment protocol and changes in fecal incontinence symptoms
- -To evaluate patient satisfaction and usability of the smartphone application component of the Leva Pelvic Health System (mHealth App Usability Questionnaire)
- To characterize parameters of product use, including adherence, coach interaction, and pelvic floor muscle parameters (endurance, lift angle)
- To evaluate self-continuation of pelvic floor muscle exercises, at 16 and 24 weeks.
- To monitor and report on safety and adverse events

### Sample Size Justification:

Treatment response as length of use on symptom improvement (8 weeks vs 16 weeks) (St Mark's (Vaizey) scores of  $-3 \pm 4.37$  at 8 weeks (compared to baseline)

- 1. Non-inferiority test (8 weeks vs 16 weeks) with allowable difference of 1 (based on statistical considerations and clinical judgement)
- 2. 8 weeks vs 16 weeks of Leva use
  - a. α =0.05
  - b. power 80%
    - i. Sample size to enroll in each group with attrition rate 20%, n= 19

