|                           | To assess whether 8 weeks of use of the Leva Pelvic Health System is non-
inferior to 16 weeks of use for the treatment of fecal incontinence in women
assessed by the St.Mark's/Vaizey score at 24 weeks.
To evaluate the relationship between adherence to the Leva Pelvic Health
System treatment protocol and changes in fecal incontinence symptoms
To evaluate patient satisfaction and usability of the smartphone application
component of the Leva Pelvic Health System (mHealth App Usability
Questionnaire – MAUQ) 
To characterize parameters of product use, including adherence, coach
interaction, and pelvic floor muscle parameters (endurance, lift angle)
To evaluate self-continuation of pelvic floor muscle exercises, at 16 and 24 |
|                           | weeks.  |

|                     | To monitor and report on safety and adverse events   |  |  |  |  |
|---------------------|--|--|--|--|--|
|                     | To evaluate long-term impact 1 year and 2 years from enrollment  |  |  |  |  |
| Research            | The Leva Pelvic Health System is a digital therapeutic system that is FDA-   |  |  |  |  |
| Intervention(s)/    | cleared for the treatment of chronic fecal incontinence (symptoms >/= 3  |  |  |  |  |
| Investigational     | months), for stress, urgency, and mixed urinary incontinence, and for pelvic   |  |  |  |  |
| Agent(s)            | floor muscle strengthening, in adults with a vagina. The system includes an intra-vaginal device that pairs with a smartphone application to provide real-
time visual feedback about pelvic floor muscle performance during usage. It is commercially available by prescription. |  |  |  |  |
| Drugs/devices used  | Leva Pelvic Health System  |  |  |  |  |
| on study (including |  |  |  |  |  |
| any IND/IDE #)      |  |  |  |  |  |
| Study Population    | Females with chronic fecal incontinence  |  |  |  |  |
| Sample Size         | 38 (19 participants in each arm, accounting for 20% attrition)   |  |  |  |  |
| Study Duration for  | Approximately 24 weeks   |  |  |  |  |
| individual          | Participants will be invited to complete 1 and 2 year survey data  |  |  |  |  |
| participants        |  |  |  |  |  |
| Study Specific      | FI – Fecal incontinence  |  |  |  |  |
| Abbreviations/      | Leva – Leva Pelvic Health System   |  |  |  |  |
| Definitions         |  |  |  |  |  |

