## 4.0 Number of Participants

Total participants to be accrued, n = 38

Patients with fecal incontinence will be solicited for interest in participation and enrolled only if they meet inclusion / exclusion criteria.

Total number of participants excluding screening failures, n = 38

Patients with fecal incontinence will be solicited for interest in participation and enrolled only if they meet inclusion / exclusion criteria. Participants will be enrolled at consent.

Total number of participants accrued, n = 38, which accounts for attrition 20%. Participants who leave the study will not be replaced.

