### Participant Population(s) for Analysis:

Non-inferiority randomized control trial comparing 8 weeks of use of the Leva Pelvic Health System to 16 weeks of use for the treatment of fecal incontinence in women assessed by the St.Mark's/Vaizey score at 16 weeks.

Each treatment arm will be matched 1:1 for 8 weeks:16 weeks use of the Leva Pelvic Health System and randomized in a permuted block randomization technique.

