### **Statistical Methods:**

The point-estimate and the fixed-margin methods are methods of analyzing non-inferiority where the margin is defined based either on the effect estimate from the historical evidence or the limit of the confidence interval of the effect estimate that is the closest to the null effect. Statistical analysis for primary objective will likely utilize the point-estimate method, as in this method, the fraction of the effect estimate that is considered clinically significant is determined based on clinical judgement.

Treatment response as length of use on symptom improvement at 16 weeks (comparing 8 weeks vs 16 weeks of use of Leva) as assessed by St Mark's (Vaizey) scores. A difference of  $-3 \pm 4.37$  is expected at 8 weeks and 16 weeks (compared to baseline), with an allowable difference of 1.

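### The stated 80% power does not follow from the plan's own inputs: with a 1-point margin, SD 4.37 and equal expected change, 19 enrolled per arm gives about 15%

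*Combined protocol and SAP*

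**What the plan says.** Section 20.0, Sample Size Justification, gives a score change of -3 ± 4.37 at 8 weeks relative to baseline, alpha 0.05 and power 80%. The test is specified as "Non-inferiority test (8 weeks vs 16 weeks) with allowable difference of 1 (based on statistical considerations and clinical judgement"), and the result is "Sample size to enroll in each group with attrition rate 20%, n= 19".

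Statistical Methods repeats the -3 ± 4.37 and says it "is expected at 8 weeks and 16 weeks (compared to baseline), with an allowable difference of 1". It describes the likely approach to the margin as one in which "the fraction of the effect estimate that is considered clinically significant is determined based on clinical judgement".

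The Study Summary gives the total as "38 (19 participants in each arm, accounting for 20% attrition"), and section 4.0 adds: "Participants who leave the study will not be replaced". Allocation is 1:1. The primary comparison is "assessed by the St.Mark's/Vaizey score at 16 weeks follow up".

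Four things are not stated: whether alpha is one- or two-sided, the unit of the margin, whether 4.37 is an SD, and which formula produced 19.

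**The concern.** For a non-inferiority comparison of two means, the sample size depends on the ratio of the SD to the distance between the true difference and the margin. Here the SD is more than four times the margin, and the plan expects equal change in both arms. Fifteen evaluable participants per arm cannot give 80% power under those conditions.

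Non-inferiority at 16 weeks is the only primary objective, and the 80% figure is the stated justification for enrolling 38 people. If the two durations are truly equivalent and power is near 15%, the trial will fail to show non-inferiority about 85% of the time. The plan gives no rule for interpreting an inconclusive interval, so such a failure could be misread as evidence that 8 weeks is worse.

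**Working it through.** **Inputs**
- Margin 1, read as St Mark's/Vaizey points (Sample Size Justification; unit not stated).
- SD of change 4.37 (same place; the ± figure read as an SD).
- True between-arm difference 0 (Statistical Methods: the same -3 for both durations).
- Alpha 0.05 (Sample Size Justification). One-sided 0.05 is assumed because it favours the plan; one-sided 0.025 is shown as the alternative.
- Attrition 20%, no replacement (Study Summary, section 4.0): 19 × 0.8 = 15.2, so about 15 evaluable per arm.

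**Trying to reproduce 19**

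n per arm = 2 × (z₁₋α + z₁₋β)² × SD² / (distance to margin)²

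With distance 1 − 0 = 1:
- One-sided 0.05: 2 × (1.645 + 0.842)² × 4.37² = 236.1, so 237 evaluable; 237/0.8 gives 297 enrolled. The t-based calculation also gives 237.
- One-sided 0.025: 299.8, so 300 evaluable (301 by t); 300/0.8 = 375 enrolled.

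The stated 19 is not reproduced. Other routes do return it, but the documents do not show which, if any, was used:
- The within-arm -3 entered as a between-arm advantage for 8 weeks. The distance is 1 − (−3) = 4, so 236.1/16 = 14.76, rounded to 15, and 15/0.8 = 18.75, rounded to 19. (By t, 15 per arm gives 0.788, so 16 and then 20 would be needed.)
- A paired test of -3 against 0 at one-sided 0.05: 15 (power 0.811), then 19.
- A margin of one SD at one-sided 0.025: 15.70 × 1.2 = 18.84, rounded to 19. (Dividing by 0.8 instead gives 16/0.8 = 20.)

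**Power at the planned size**

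Standard error of the difference with 15 per arm: 4.37 × √(2/15) = 1.596. Normal approximation: Φ(1/1.596 − 1.645) = Φ(−1.018) = 0.154. The noncentral t gives 0.151, and simulation of the t-based confidence limit agrees (0.151 to 0.152). At one-sided 0.025 the noncentral t gives 0.088. If all 19 per arm stay evaluable, power is 0.170 (0.101).

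Put another way, the one-sided 95% limit lies 2.71 points from the estimate. The 8-week arm would have to be observed at least 1 − 2.71 = −1.71, that is 1.7 points better, for non-inferiority to be declared.

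**How far the readings matter** (15 evaluable per arm, noncentral t)

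| Reading | One-sided 0.05 | One-sided 0.025 |
|---|---|---|
| Margin 1 point, SD 4.37, difference 0 | 15% | 9% |
| 8 weeks truly 0.5 worse | 9% | 5% |
| 8 weeks truly 1 better | 34% | 23% |
| 8 weeks truly 2 better | 58% | 44% |
| 8 weeks truly 3 better | 79% | 68% |
| Margin 3 points (the whole expected change) | 58% | 44% |
| Margin one SD (4.37 points) | 85% | 75% |
| 4.37 is a variance (SD √4.37 = 2.09) | 36% | 24% |

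If 4.37 were a standard error, the SD would be larger and power lower.

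With 15 per arm and no true difference, 80% power needs a margin of 4.07 points (4.63 at 0.025). At a margin of 1 it needs an SD of about 1.07 (0.94). The plan describes no baseline adjustment. By the normal formula the SD would have to fall to 1.10, which needs a correlation of √(1 − (1.10/4.37)²) ≈ 0.97.

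**The case against.** The strongest reply is that the plan never gives the margin a unit, and its stated basis does not exclude a standardised margin. If 1 means one SD, power at 15 per arm is 85% or 75% depending on sidedness. Required enrolment by the normal formula is then 17 or 20 per arm, on either side of 19. On that reading the sample size is about right and the defect is a missing unit.

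This cannot be excluded, but it fits the text poorly. Statistical Methods puts the 1 in the same sentence as a 3-point score change, with nothing to suggest a different scale. A margin of 4.37 points would be 4.37/3 = 146% of the expected improvement, so 8 weeks could lose the whole benefit and still pass. The plan's account of setting the margin as a fraction of an effect estimate also points away from it. That last argument carries less weight, because the plan says only that it will likely use the method and does not identify -3 as the historical effect estimate.

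Two further reservations are fair. The figure comparable with 19 enrolled is 297 enrolled, not 237 evaluable. The risk that an inconclusive result is misread is a possibility; the plan does not say it would report failure that way. Neither changes the arithmetic.

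**Conclusion.** The concern holds. With a margin of 1 scale point, SD 4.37 and the equal change the plan expects, 19 enrolled per arm gives about 15% power at one-sided 0.05, or 9% at 0.025. It does not give 80%. The shortfall in enrolment is 19 against 297 per arm (375 at 0.025). Neither choice of sidedness, nor full retention, nor reading 4.37 as a variance brings power above 36%.

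The result rests on three readings the plan leaves unlabelled: the margin is in points, 4.37 is the SD of change, and the true difference is 0. The two readings that approach 80% each conflict with Statistical Methods: the one-SD margin with how it presents the margin, and the 3-point advantage for 8 weeks with its expectation of equal change. How 19 was obtained is unknown, and the conclusion does not depend on it. The power statement has to be corrected before the primary analysis.

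**What to change.** 1. In Sample Size Justification, state the inputs actually used: sidedness of alpha, unit of the margin, what ± 4.37 represents, and the assumed true between-arm difference. Reconcile them with Statistical Methods.
2. Unless different inputs are documented, replace the 80% claim with text such as: *With 15 evaluable per arm, SD 4.37, true difference 0 and one-sided alpha 0.05, power for a margin of 1 point is about 15%; 80% power is available only for a margin of about 4 points.* At one-sided 0.025 the figures are about 9% and 4.6 points. The margin should not be widened to about 4 points to match the sample, because that exceeds the expected 3-point improvement.
3. Optionally, add a decision rule to Statistical Methods. With positive values meaning 8 weeks is worse, an upper confidence limit below 1 shows non-inferiority. An interval that includes 1 is inconclusive for non-inferiority and is not by itself evidence that 8 weeks is worse.

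The cost is a protocol amendment and a much less favourable stated power for the primary objective. No extra participants, visits or data are needed, and the text can be corrected at any time before the primary analysis.

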### Participant Population(s) for Analysis:

Non-inferiority randomized control trial comparing 8 weeks of use of the Leva Pelvic Health System to 16 weeks of use for the treatment of fecal incontinence in women assessed by the St.Mark's/Vaizey score at 16 weeks.

Each treatment arm will be matched 1:1 for 8 weeks:16 weeks use of the Leva Pelvic Health System and randomized in a permuted block randomization technique.

### **Statistical Methods:**

The point-estimate and the fixed-margin methods are methods of analyzing non-inferiority where the margin is defined based either on the effect estimate from the historical evidence or the limit of the confidence interval of the effect estimate that is the closest to the null effect. Statistical analysis for primary objective will likely utilize the point-estimate method, as in this method, the fraction of the effect estimate that is considered clinically significant is determined based on clinical judgement.

Treatment response as length of use on symptom improvement at 16 weeks (comparing 8 weeks vs 16 weeks of use of Leva) as assessed by St Mark's (Vaizey) scores. A difference of  $-3 \pm 4.37$  is expected at 8 weeks and 16 weeks (compared to baseline), with an allowable difference of 1.

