### Primary endpoint

• The reduction in fecal incontinence severity measured at 16 weeks following 8 weeks of use of the Leva Pelvic Health System will be non-inferior to the reduction in fecal incontinence severity following 16 weeks of use of the Leva Pelvic Health System as measured by the St. Mark's/Vaizey score.

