### Planned Interim Analysis

No interim efficacy analysis is planned.

Device usage data and safety data will be collected throughout the study period. The anticipated risk is minimal; the study team will alert the investigator if responses to surveys about quality of life indicate concerns for participant well-being.

Complete efficacy data will be collected at 16 weeks and at 6 months from study start for comparison to baseline data.

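### The primary analysis is provisionally a margin-setting method; no between-arm estimator, confidence level or confidence-limit rule is stated, and the week-0 St Mark's score is not used for adjustment

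*Combined protocol and SAP*

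**What the plan says.** All of this is in Section 20.0 unless stated.

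- **Method.** Statistical Methods introduces the point-estimate and fixed-margin approaches as "methods of analyzing non-inferiority where the margin is defined based either on the effect estimate from the historical evidence", or on a confidence limit of that estimate. It then says: "Statistical analysis for primary objective will likely utilize the point-estimate method". The reason given is that clinical judgement sets the fraction of the effect that counts. The source cited there (reference 15) is a systematic review of ways to define the margin.
- **Test, margin and level.** Sample Size Justification gives "Non-inferiority test (8 weeks vs 16 weeks) with allowable difference of 1 (based on statistical considerations and clinical judgement", with alpha 0.05 and 80% power. Sidedness is not stated.
- **Endpoint.** Section 3.0 gives "The reduction in fecal incontinence severity measured at 16 weeks following 8 weeks of use", compared with the reduction after 16 weeks of use. Planned Interim Analysis adds: "Complete efficacy data will be collected at 16 weeks and at 6 months from study start for comparison to baseline data". The endpoint therefore reads as change from baseline to week 16. Section 13.0 confirms that the St Mark's score is collected at week 0.
- **Expected result.** Statistical Methods expects -3 ± 4.37 from baseline at both 8 and 16 weeks.
- **Analysis population.** The subsection with this title gives the comparison and says that arms are "randomized in a permuted block randomization technique". It names no analysis set.

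**The concern.** Setting a margin and testing against it are separate steps. The margin is already fixed at 1 point, so deriving it cannot also be the test. What the plan needs is an estimate of the difference between arms, an interval at a stated level, and a rule saying which limit must fall on which side of 1. None of these is stated, and the one method named is tentative.

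Two consequences follow. First, the name invites a misreading, namely that non-inferiority needs only an observed difference below 1. Nothing in Section 20.0 expressly excludes that reading, and it would carry a 50% error rate at the margin. Second, a free gain is left unused. The baseline score is already collected, and adjusting for it usually narrows the interval, which is wide relative to a 1-point margin.

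**Working it through.** **1. Which alpha produced the plan's sample size?** The plan states "Sample size to enroll in each group with attrition rate 20%, n= 19", and Section 1.0 agrees: "38 (19 participants in each arm, accounting for 20% attrition". Inputs are SD 4.37, 80% power (z = 0.842) and 20% attrition. With the normal approximation, n per arm = 2 × SD² × (z_alpha + z_power)² / distance².

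| Distance to margin | One-sided alpha | Evaluable per arm | Enrolled per arm |
|---|---|---|---|
| 4 (margin 1 plus 3) | 0.05 | 2 × 4.37² × (1.645 + 0.842)² / 4² = 14.76, so 15 | 15/0.8 = 18.75, so **19** |
| 4 | 0.025 | 18.74, so 19 | 19/0.8 = 23.75, so 24 |
| 1 (equal arms) | 0.05 | 237 | 297 |
| 1 (equal arms) | 0.025 | 300 | 375 |

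Only the first row gives 19 after attrition. It does so by entering the -3 change from baseline as if it were a 3-point advantage of 8 weeks over 16. The match also needs the normal approximation; with the t distribution, 16 evaluable and 20 enrolled are needed. The row points to one-sided 0.05 as the level used. It does not validate the sample size.

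**2. Unadjusted change score.** Take 4.37 as the SD of change (the documents do not say what ± is) and 15 evaluable per arm.

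- Standard error = 4.37 × √(2/15) = 1.596.
- 90% half-width = 1.701 × 1.596 = 2.71. The observed 8-minus-16-week difference must be below 1 - 2.71 = -1.71 to pass.
- 95% half-width = 2.048 × 1.596 = 3.27.
- Power at a true difference of 0, one-sided 0.05 (noncentral t): 15.1%.

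**3. ANCOVA.** Assume equal SDs at weeks 0 and 16 and correlation rho between them; neither is in the documents. Raw-score SD = 4.37/√(2(1 - rho)). Variance relative to the change score = (1 + rho)/2 × [1 + 1/(30 - 4)], where the bracket (1.038) is the small-sample cost of one covariate.

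| rho | Implied raw SD | Variance ratio | 90% half-width | 95% half-width | Power (one-sided 0.05) |
|---|---|---|---|---|---|
| 0.3 | 3.7 | 0.675 | 2.23 | 2.69 | 18.4% |
| 0.5 | 4.4 | 0.779 | 2.40 | 2.89 | 17.0% |
| 0.7 | 5.6 | 0.883 | 2.55 | 3.08 | 16.0% |
| 0.9 | 9.8 | 0.987 | 2.70 | 3.25 | 15.2% |

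For example, at rho 0.5 the residual SD is 4.37 × √0.75 = 3.785, and 1.703 × 3.785 × √(2/15 × 1.038) = 2.40.

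**4. Unequal SDs.** With k = week-16 SD / week-0 SD, the ratio is k²(1 - rho²)/(1 + k² - 2 rho k) × 1.038. For rho 0.3, 0.5, 0.7 and 0.9:

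- k = 0.8 gives 0.521, 0.593, 0.652 and 0.631.
- k = 1.2 gives 0.791, 0.904, 1.003 and 1.015. The worst case is thus 1.5% more variance.

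**5. Rule on the observed difference alone.** At a true difference of 1, the estimate falls below 1 half the time, so the error is 50%. At a true difference of 0 the pass rate is Φ(1/1.596), about 73%. Under the 90% upper-limit rule these rates are 5% and about 15%.

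**The case against.** **The plan does intend to compare the arms.** It labels these approaches as ways of analysing non-inferiority, and the next paragraph refers to comparing 8 with 16 weeks of use. A reader might infer that the named method leaves the arms uncompared. The documents do not support that; the comparison is intended, and its procedure is what is missing.

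**Sidedness is less open than it looks.** Alpha is attached to a non-inferiority test with directional hypotheses, so one-sided 0.05 is the natural reading, and the other candidate is stricter. A reader might infer that this ambiguity lets error exceed 5%. It cannot do so by itself. The confidence level still has to be written down, because the supporting back-calculation rests on a misplaced input.

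**Harm from an open estimator is hypothetical.** In simulation (100,000 trials per correlation, 15 per arm, true difference 1), taking the more favourable of change score and ANCOVA gave false non-inferiority of 7.4% to 6.0% over rho 0.3 to 0.9. That assumes selective reporting, and nothing in the documents suggests it is planned. Nor do they say that the sponsor would decide on the observed difference alone; that reading is merely not excluded.

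**ANCOVA is a preference.** This stands in part. The endpoint is worded as a reduction, so a difference in mean change is closest to the text, and prespecifying it with the same limit rule would close the gap. ANCOVA targets the same between-arm contrast and is usually more precise, but its gain depends on figures the documents do not give.

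**Assigned-arm analysis does not settle missing week-16 scores.** This also stands. Section 15.0 ends data collection at withdrawal, and Handling of Missing Data leaves the model open.

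**Conclusion.** The point holds as a low-cost improvement that should be made before analysis. A margin-setting method is provisionally named as the primary analysis. Estimator, confidence level and limit-against-margin rule are absent, and the baseline score is not used.

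The gain from ANCOVA is a variance reduction of 32% to 1% and a 90% half-width of 2.23 to 2.70 instead of 2.71 points. It rests on reading ± 4.37 as the SD of change, 15 evaluable per arm (19 less 20%), and the assumed equal SDs and correlation of 0.3 to 0.9. The explicit rule matters at least as much, because it closes off the 50%-error reading.

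A reader might infer that the fix makes the trial adequate for a 1-point margin. It does not: power at a true difference of 0 stays between 15% and 18%. The clash between the 19 per arm and the equal changes expected in Statistical Methods is a separate, larger problem.

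**What to change.** Keep the point-estimate wording only as the rationale for the margin of 1, and replace the sentence on the primary analysis with:

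*The primary analysis is an ANCOVA of the week-16 St Mark's score on arm and baseline St Mark's score, with participants analysed in their assigned arm; non-inferiority is concluded if the upper limit of the two-sided 90% CI (one-sided alpha 0.05) for the adjusted 8-minus-16-week difference is below 1 point.*

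If the sponsor intended one-sided 0.025, write 95% instead; one level must be fixed before analysis. Use the same model and rule for the 24-week St Mark's non-inferiority objective. State alongside it how participants without a week-16 score are handled.

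The cost is a few sentences in Section 20.0, with no new data, visits or participants. Statistically, it is one degree of freedom (about 4% of variance at 15 per arm, already counted above). The gain nearly vanishes at correlation 0.9. Variance rises by 0.3% to 1.5% at correlations of 0.7 to 0.9 if the week-16 SD is 20% larger than at baseline.
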